2.3 Methodology /Technical Approach

Subjects that meet study inclusion criteria will be recruited from the Adult and Pediatric Gastroenterology clinics at WRNMMC through routine clinic visits, will meet with an investigator, and complete informed consent/assent. The participants will then complete a validated clinical symptom reporting tool - the Eosinophilic Esophagitis symptom activity index (EEsAI) for age 18 and above, or the Pediatric Quality of Life Inventory (PedsQL) for age 6-17yrs - and have their initial Esophagogastroduodenoscopy (EGD) images evaluated via a validated Endoscopic Reference Score (EREFS). Esophageal biopsies taken at patients initial EGD will be assessed by 2 designated blinded pathologists to record the number of eosinophils per high power field (HPF), as well as perform tissue immunohistochemical staining for eotaxin-3. Participants will be block randomized to treatment or control groups and complete 8 weeks of therapy, with a phone follow up at 4 weeks. At completion of 8 weeks of therapy, the participants will have repeat EGD with EREFs, biopsies evaluated for eosinophils/hpf and eotaxin-3 staining, and repeat EEsAI/PedsQL. We estimate a sample size of approximately 100 subjects.

9.2 Key Words:

Provide up to 5 key words that identify the broad topic(s) of your study

9.3 Background and Significance:

Include a literature review that describes in detail the rationale for conducting the study. Include descriptions of any preliminary studies and findings that led to the development of the protocol. The background section should clearly support the choice of study variables and explain the basis for the research questions and/or study hypotheses. This section establishes the relevance of the study and explains the applicability of its findings

Literature Review.

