The participants who choose to consent and enroll in the study will then complete either the EEsAI (age 18 -60) or the PedsQL (age 6-17), both validated questionnaires that assess patient symptoms of EoE. Additionally, all study participants will have their initial Esophagogastroduodenoscopy (EGD) images evaluated via Endoscopic Reference Score (ERFS). This scoring system is a validated tool that has demonstrated moderate to good inter-observer variability. The PI for this protocol will be the physician who assigns a score to pre and post intervention images, in order to limit variations between graders. The 6-8 esophageal biopsies taken at initial EGD will be evaluated by pathology per routine protocol to provide primary diagnosis. Again to limit variation, there are two pathologists serving on this protocol as AIs that will be evaluating the specimens obtained during this research period. Each set of biopsies will then be evaluated by 1 of these 2 pathologists to record the number of eosinophils per high power field (HPF). Immunohistochemical staining on these biopsies for eotaxin-3 will be performed on the Ventana Ultra platform after stain optimization based on previously described protocols. Staining will be evaluated by 1 of 2 pathologists for intensity and percentage of cells staining (Allred scoring system). [name] will be performing research as a credentialed provider at WRNMMC Department of Pathology, although he is assigned to Joint Pathology Center.

The participants will be randomized into 2 groups: 1) omeprazole + swallowed fluticasone and 2) placebo + swallowed fluticasone. The placebo will replicate oral omeprazole. The study participants will be randomly assigned with concealment of allocation to one of the treatment groups, with each group having an equal number of participants (1:1 ratio).

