Each treatment group will be treated for 8 weeks. Therapy for the PPI + topical steroid group will be 40mg omeprazole by mouth twice daily and 880mcg swallowed fluticasone twice daily. Therapy for the placebo + topical steroid group will be a sham omeprazole capsule by mouth twice daily and 880mcg nebulized and swallowed fluticasone twice daily (total dosage 1760 mcg). Participants will be instructed to take omeprazole or placebo on an empty stomach each morning, at least 30 minutes prior to eating, but no more than 60 minutes. Participants will also be instructed to rinse mouth with water or brush teeth after taking fluticasone, but not swallow anything within 30 minutes after taking the medication. For study participants age 17 years and younger, the dose for fluticasone will be 440mcg given 2-4 times per day based on 2011 consensus guidelines.(1) The pediatric dose for omeprazole will be 2mg/kg/day divided twice daily, with max dose of 40mg per day.

Compliance will be checked via phone follow up at 4 weeks and in person at 8 weeks (completion of therapy) by asking patient to report number of pills remaining and number of actuations remaining on the MDI. Participants will be given enough medication to last the full 8 weeks of therapy. At the time of repeat endoscopy, patients will be instructed to bring their medications for a full count of remaining pills.

At the end of 8 weeks of therapy, participants will undergo repeat EGD, with re-evaluation of all markers completed at the start of therapy including esophageal eosinophilia, endoscopic assessment (EREFS), validated clinical questionnaire (EEsAI or PedsQL), and immunohistochemistry staining for eotaxin-3. EGDs will be performed to standard of care, with biopsies taken from the esophagus only.

Prior to the EGDs, all pediatric subjects will undergo the routine pre-op evaluations and physicals by Pediatric GI and anesthesia, which is standard of care. All subjects are required to fast beginning the night prior to the EGD which is also standard practice.

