If the study involves collecting, storing, or banking human specimens, data, or documents (either by the Investigator or through an established repository) for FUTURE research, address. How the specimens /data will be used, where and how data/specimens will be stored (including shipping procedures, storage plan, etc.), whether and how consent will be obtained, procedures that will fulfill subjects' request as stated in the consent, whether subjects may withdraw their data/specimens from storage, whether and how subjects may be recontacted for future research and given the option to decline, whether there will be genetic testing on the specimens, who will have access to the data/specimens, and the linkage, the length of time that data/specimens will be stored and conditions under which data/specimens will be destroyed.

The specimens and data collected during the study period will be accessible to the researcher for future research studies if the subject provides consent. The data will be stored for a 10 year period in a de-identified file as described above. According to the standard operating procedure of the Pathology Department, the specimens will be kept with patient identifiers for a period of 10 years. The researcher will not extend this period or make any changes to the protocol. Subjects may withdraw their data and specimens at any time. The subjects will not be contacted for future research, unless requested. There will not be any genetic testing done on these specimens.

11.0

Statistical/Data Analysis Plan

11.1 Statistical Considerations:

List the statistical methods to be used to address the primary and secondary objectives, specific aims, and/or research hypotheses. Explain how missing data and outliers will be handled in the analysis. The analysis plan should be consistent with the study objectives. Include any sub-group analyses (e.g., gender or age group). Specify statistical methods and variables for each analysis. Describe how confounding variables will be controlled in the data analysis

See 11.4 below.

11.2 Sample Size:

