The sample size was estimated for the primary outcome utilizing a two-sided likelihood ratio chi-square test of two independent proportions. The following parameters were used in this calculation: alpha of 0.05 and a power of 0.80. A response rate in the control group of fluticasone alone (reference proportion) was estimated to be 50% based on the study Konikoff et al.⁶ The estimated response rate for the treatment arms are based on clinical experience as was estimated to be in the range of 70% to 80%. This graph demonstrates that the sample size estimation may vary anywhere from 78 to 180 subjects. We plan to enroll approximately 100 patients.

11.3 Total number of subjects requested (including records and specimens):

100

11.4 If you are recruiting by study arm, please identify the arms of the study and how many subjects will be enrolled in each arm

50 subjects in each arm - one arm will be fluticasone and placebo, one arm will be fluticasone and omeprazole.

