11.5 Please provide a justification for your sample size

The sample size was estimated for the primary outcome utilizing a two-sided likelihood ratio chi-square test of two independent proportions. The following parameters were used in this calculation: alpha of 0.05 and a power of 0.8. A response rate in the control group of fluticasone alone (reference proportion) was estimated to be 50% based on the study Konikoff et al (6). The estimated response rate for the treatment arms are based on clinical experience as was estimated to be in the range of 70% to 80%. This graph demonstrates that the sample size estimation may vary anywhere from 78 to 180 subjects. We plan to enroll approximately 100 patients.

11.6 Data Analysis Plan:

Outcome variables are listed in the following table. All continuous data will be evaluated for normality of the data using both univariate methods, visual inspection, and the Kolmogorov Smirnov test. Differences in continuous data that is normally distributed will be tested using parametric tests and for data that is not normally distributed a nonparametric test. Likert scale data will be transformed into numerical data and evaluated as continuous variables.

Outcome variables	Variable Type	Statistical Test
Primary Outcome Tissue esophageal eosinophils < 15/ hpf	Binary categorical	Two-sided likelihood ratio chi-square test of two independent proportions

Change in EEsAI	Likert scale - continuous	Normally distributed data: t-test Non-normally distributed data: Mann-Whitney U
Change in PedsQL	Likert scale - continuous	Normally distributed data: t-test Non-normally distributed data: Mann-Whitney U
Change in EREFS	Continuous	Normally distributed data: t-test Non-normally distributed data: Mann-Whitney U
Change in eosinophils per hpf	Continuous	Normally distributed data: t-test Non-normally distributed data: Mann-Whitney U
Change in tissue eotaxin level	Continuous	Normally distributed data: t-test Non-normally distributed data: Mann-Whitney U

Although all outcomes will be evaluated and reported using pooled data, a priori planned subgroup analysis will include a stratification of the analysis and results based on adult and pediatric subject groups.

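### Age group sets both drug regimens and is the one named subgroup, yet no age strata are stated for randomisation, the primary test ignores age, and no adult–child comparison is specified: a cheap improvement

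*Combined protocol and SAP*

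**What the plan says.** **Randomisation.** Section 2.3 states "Participants will be block randomized to treatment or control groups and complete 8 weeks of therapy". Section 10.1 adds concealed allocation at 1:1, and 11.4 gives "50 subjects in each arm - one arm will be fluticasone and placebo, one arm will be fluticasone and omeprazole". None of these names a stratification factor. Section 14.3 builds subject codes from adult or paediatric status and recruitment order, but presents this as confidentiality coding, not as a randomisation rule.

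**Age group.** Section 10.1 gives adults and children different regimens for both drugs. For fluticasone, for example: "For study participants age 17 years and younger, the dose for fluticasone will be 440mcg". Omeprazole is weight-based in children and fixed in adults. The symptom questionnaire also depends on age: EEsAI for adults, PedsQL for children.

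**Analysis.** The primary outcome (fewer than 15 eosinophils per high power field) is both sized and analysed with a "two-sided likelihood ratio chi-square test of two independent proportions" (11.2, 11.5, 11.6). Section 11.6 says "all outcomes will be evaluated and reported using pooled data" and that "a priori planned subgroup analysis will include a stratification of the analysis and results based on adult and pediatric subject groups". It names no covariate and no method for comparing the two age groups.

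**Confounders.** The form in 11.1 instructs: "Describe how confounding variables will be controlled in the data analysis". The reply only sends the reader to 11.4, which holds the arm sizes. The methods are in 11.6.

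**The concern.** If adults and children respond at different rates, a chance difference in age mix between the arms moves the pooled treatment difference, and an unadjusted test gives up some precision. Stating strata and using them in the analysis avoids both.

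The subgroup analysis is the more practical matter. Results will be shown separately for adults and children, who take different regimens, with roughly 25 patients per arm in each group and no stated comparison between them. One significant and one non-significant result would invite the reading that the combination works in only one age group. That pattern is common even when the effect is identical in both.

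**Working it through.** **Inputs from the plan.** 50 per arm; two-sided alpha 0.05; control response 50%; treated response 70% to 80% (11.2, 11.4, 11.5).

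**Assumptions.** 50 adults and 50 children, with a 30:70 split as a second case; a gap of 0 to 40 points between the age groups' response rates. The plan gives neither figure. The background in 9.3 reports similar histologic improvement in adults, so large gaps are an upper range.

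**1. The plan's own figure.** The likelihood ratio (LR) chi-square, by its non-central approximation, needs 78 in total for 50% vs 80%, which matches the plan. For 50% vs 70% it gives 188 against the stated 180, which is read from a graph not shown; nothing below depends on this. Exact power at 50 per arm is 0.545, 0.745 and 0.895 for 70%, 75% and 80%.

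**2. Chance imbalance.** With A adults among 100 patients, the number X in one arm is hypergeometric (100, A, 50), and the arms differ by |2X − A| adults.

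| Adults | P(differ by ≥6) | ≥8 | ≥10 |
|---|---|---|---|
| 50 | 0.317 | 0.161 | 0.071 |
| 30 | 0.275 | 0.126 | 0.049 |

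Shift in the pooled difference = (imbalance / 50) × age gap. For 8 adults, 8/50 = 0.16, so gaps of 10, 20 and 30 points shift it by 1.6, 3.2 and 4.8 points.

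**3. Power.** Simulation with 200,000 trials per cell, unstratified allocation, 50:50 split and the same risk difference in both age groups. Each cell shows planned LR test / CMH test by age group.

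| True effect | Gap 0 | 10 | 20 | 30 | 40 |
|---|---|---|---|---|---|
| 20 points | 0.545 / 0.536 | 0.545 / 0.538 | 0.545 / 0.550 | 0.545 / 0.575 | 0.547 / 0.613 |
| 25 points | 0.747 / 0.742 | 0.745 / 0.745 | 0.746 / 0.760 | 0.745 / 0.786 | 0.745 / 0.822 |
| 30 points | 0.894 / 0.892 | 0.895 / 0.897 | 0.895 / 0.908 | 0.894 / 0.927 | 0.893 / 0.952 |

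The last cell requires 100% response in the better group. With a 30:70 split the changes are −1 to +1 points at gaps of 0 to 20, +2 to +3 at 30 and +5 to +7 at 40. If the odds ratio rather than the risk difference is common to both groups, the gains are somewhat smaller: for 50% vs 70% at a 40-point gap, 0.546 becomes 0.596. With stratified lists as well, CMH at zero gap gives 0.546, 0.746 and 0.895, so essentially nothing is lost.

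**4. Type I error.** The planned test runs at 0.057 to 0.058 at every gap. CMH runs at 0.049 to 0.052 with unstratified lists and roughly 0.05 to 0.06 with stratified lists. If the lists are stratified but the test stays pooled, the error falls to about 0.046 at a 30-point gap and 0.038 at a 40-point gap.

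**5. Subgroups.** Exact power p of the LR test at 25 per arm, and the chance 2p(1 − p) that exactly one of the two age groups is significant when the effect is the same in both:

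- 50% vs 70%: p = 0.334; 2 × 0.334 × 0.666 = 0.445
- 50% vs 75%: p = 0.479; 2 × 0.479 × 0.521 = 0.499
- 50% vs 80%: p = 0.638; 2 × 0.638 × 0.362 = 0.462

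With 15 and 35 per arm (30:70 split) the three chances are 45%, 54% and 55%.

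**6. Interaction estimate.** On the risk-difference scale with 25 per cell, SE = √(Σ p(1 − p)/25) over the four cells. With both control rates at 50% and treated rates of 60% and 80%: √((0.25 + 0.25 + 0.24 + 0.16)/25) = 0.190, so the 95% interval is ±1.96 × 0.190, about ±37 points. Across plausible cell rates, power is about 17% to 19% for a 20-point difference in effect. For a 30-point difference it is 35% (SE 0.191).

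**The case against.** The strongest reply is that a pooled, unadjusted test that matches the sizing test is a legitimate choice, and that no document supports the 30- to 40-point age gaps at which CMH clearly gains. This stands: for the primary test alone the benefit is probably small.

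Imbalance and lost precision are also one harm seen twice. The shifts in step 2 are already averaged into the power in step 3, and the planned test's type I error does not rise with the age gap. That stands too, and the two should not be added together.

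The power comparison is not matched on size (about 0.057 against about 0.050). This is true, but it works against CMH, so the apparent 1-point cost at zero gap is partly the LR test's extra type I error.

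Section 11.6 does not say that the subgroup p-values will be compared, so the subgroup harm presumes a misreading. This is fair, but the plan offers nothing else by which to compare the groups. The proposed interaction test has low power and resolves little; its value is in showing how uncertain the difference is.

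Finally, the cross-reference in 11.1 is clerical, and a randomised trial does not need a covariate to be valid. Both are granted.

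**Conclusion.** The concern holds as a recommended improvement, not an error. The planned primary test is approximately valid. Stratifying by age is worth little if adults and children respond within 20 points of each other (−1 to +1.4 points of power with the analysis change alone). It is worth 3 to 4 points at a 30-point gap and 6 to 8 at a 40-point gap. These figures assume a 50:50 age split and a common risk difference; a 30:70 split gives slightly smaller gains.

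The firmer part is the subgroup analysis, which needs no age gap. At 50:50, results read side by side would disagree on significance in 45% to 50% of trials with identical true effects, and a 30:70 split is no better. Stratification does not cure the low subgroup power.

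**What to change.** - **2.3 and 10.1:** state separate block lists for adults (18 and over) and children (6 to 17).
- **11.6, primary outcome:** use a CMH test stratified by age group, with a stratified risk difference and 95% confidence interval. Make this change together with the lists, because stratified lists with a pooled test are conservative when age is strongly prognostic.
- **11.6, other outcomes:** adjust for age group where the measure exists in both groups (EREFS, eosinophil count, eotaxin-3).
- **11.6, subgroup:** report a treatment-by-age-group interaction estimate with its confidence interval, state its low power, and draw no conclusion from separate p-values.
- **11.1:** point to 11.6 instead of 11.4.

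If allocation has begun, adopt the analysis changes alone, before unblinding.

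**Cost:** one extra randomisation list and a few sentences. No more patients or data are needed, since age is already recorded. If age turns out not to matter, power falls by at most about 1 point with the analysis change alone, and by about 0.1 point or less with both changes.

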The EGDs will be performed according to standard of care. All pediatric patients undergoing EGD for evaluation of symptoms consistent with abdominal pain, dysphagia, vomiting, poor weight gain, etc., have the same endoscopic investigation and biopsy specimens obtained, regardless of what is seen. It is also standard of care for all adult subjects presenting with symptoms suggestive of EoE (dysphagia, food impaction) to undergo upper endoscopic evaluation with esophageal biopsies. Biopsy specimens will be sent to pathology for standard histological examination. A single pathologist will be assigned to review all of the slides and corroborate the findings on any abnormal results.

EGDs will be performed using Olympus GIF140 or 160 endoscopes. Each subject will undergo all the standard pre-operative evaluations including physicals done by the pediatric GI provider and anesthesia. The type of sedation or general anesthesia will be based on the assessment by the anesthesia team responsible for the subject during the EGD. All pediatric patients undergoing an EGD will have the same endoscopic evaluation regardless of the indication for the procedure. It is standard practice to obtain biopsies from the duodenum, stomach and esophagus during the initial EGD, however, follow up EGDs will include only esophageal biopsies.

Esophageal biopsy specimens sent to pathology will be examined and reviewed by the pathologists. For each subject, the specific number of eosinophils per high power field (HPF) will be collected. As previously mentioned, 1 of 2 participating pathologists will be assigned to review all the slides, and corroborate the specific number of eosinophils. This data is also documented as part of the subjects routine care, and thus the results will be maintained in the AHLTA electronic record system as well. As an additional outcome measure, tissue eotaxin-3 level, will be measured independently by 1 of 2 pathologists on all subjects.

Assessment	Visit/Follow up Interval				
	Day of identification	Within 2 weeks of consent	Week 4	Week 8	Week 8-10
Screening/Informed consent /Discuss plan	X				
Randomization	X				
Demographics	X				
Pt completes clinical questionnaire	X				
Begin treatment	X				
PI/AI reviews initial endoscopy findings		X			

Path stain esophageal tissue for eotaxin-3		X			
Phone follow up for compliance check			X		
EGD				X	
Pt completes clinical questionnaire				X	
Path stain for eotaxin-3 on repeat biopsies					X

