PI/AI reviews repeat endoscopy findings					X

10.2 Data Collection:

Describe all the data variables, information to be collected, the source of the data, how the data will be operationally measured, and approvals needed for use of information from DoD databases

Method of Collection from Study Participants.

- EEsAI or PedsQL (approval received for research use) standardized symptom questionnaires, based on age of participant, will be used to assess participant symptoms prior to treatment.
- Initial Esophagogastroduodenoscopy (EGD) images will be evaluated via Endoscopic Reference Score (EREFS) by investigators.
- Biopsies taken at initial EGD will be evaluated by pathology for number of eosinophils per high power field (HPF) and tissue eotaxin-3 level.
- Compliance will be checked via phone follow up at 4 weeks, and in person at 8 weeks (completion of therapy) by asking patient to report number of pills remaining and number of actuations remaining on the MDI.
- Participants will be given enough medication to last the full 8 weeks of therapy.
- At the end of 8 weeks of therapy, participants will undergo repeat EGD, with re-evaluation of all markers completed at the start of therapy: EREFS, EEsAI or PedsQL, and tissue for number of eosinophils per HPF and eotaxin-3 staining.

Study variables

- a. Independent
 1. Standard therapy treatment group: Fluticasone topical steroid
 2. Intervention treatment group: Fluticasone topical steroid + PPI
- b. Dependent
 1. EEsAI/PedsQL

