Describe in detail the plan to maintain confidentiality of the research data, specimens, and records throughout the study and at its conclusion (e.g., destruction, long term storage, or banking). Explain the plan for securing the data (e.g., use of passwords, encryption, secure servers, firewalls, and other appropriate methods). If data will be shared electronically with other team members/collaborators outside the institution, describe the method of transmission and safeguards to maintain confidentiality. Explain whether this study may collect information that State or Federal law requires to be reported to other officials or ethically requires action, e.g., child or spouse abuse

All hard copies of data will be kept in a locked file cabinet in the office of the PI at WRNMMC. The spreadsheet with EEsAI or PedsQL scores, EREFS score, histology and demographics will not include any names of the subjects, and will only be identified by numeric code. These codes will be randomly assigned by the PI, and the subjects identity will be stored electronically on the PIs password protected computer. Each unique subject code will be determined by whether they are an adult or pediatric subject, and their general chronological order of recruitment using only odd or even numerals (ie, P-5, A-22). All codes will be alphanumeric in nature.

All data will be stored and organized on a spreadsheet table. An alpha-numeric code will be assigned to each subject who will be used to identify the subject on the spreadsheet table. The PI will assign these codes, and PI and Research Monitor will only have access to the subject identifier codes on a master list. The research file will be stored electronically on the PIs password protected computer. The master list will be destroyed 5 years after study completion. All de-identified data related to the study will be destroyed 10 years after study completion.

14.4

Potential Benefits:

Describe any real and potential benefits of the research to the subject and any potential benefits to a specific community or society

If the individuals in the research are considered experimental subjects (per 10 USC 980), and they cannot provide their own consent, the protocol must describe the intent to directly benefit all subjects

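### Nothing requires week-8 EREFS to be scored before the grader can see that subject's week-8 biopsy and symptom results, so EREFS may partly echo histology

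*Combined protocol and SAP*

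**What the plan says.** **Who grades.** Section 10.1 names the principal investigator (PI) as EREFS grader: "The PI for this protocol will be the physician who assigns a score to pre and post intervention images". The stated purpose is "in order to limit variations between graders"; masking is not mentioned. Other text is looser. The visit schedule in 10.1 has "PI/AI reviews repeat endoscopy findings", and section 10.2 assigns the initial images to investigators in the plural.

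**What the PI holds.** Section 14.3 describes one file: "The spreadsheet with EEsAI or PedsQL scores, EREFS score, histology and demographics will not include any names of the subjects". On its custody: "The research file will be stored electronically on the PIs password protected computer". On paper records: "All hard copies of data will be kept in a locked file cabinet in the office of the PI at WRNMMC". On the key: "The PI will assign these codes, and PI and Research Monitor will only have access to the subject identifier codes on a master list". Coding therefore does not mask the PI. By another route, section 10.1 says of eosinophil counts that "the results will be maintained in the AHLTA electronic record system as well".

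**When.** The schedule places the repeat EGD and questionnaire at week 8. Review of the repeat endoscopy is in the week 8-10 column, alongside eotaxin-3 staining of the repeat biopsies.

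**Who is blinded.** The trial is double-blind to treatment (9.5). The methodology summary in 9.1 calls the pathologists blinded. No section says what the EREFS grader may or may not know about the other outcomes.

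**Role of EREFS.** Endoscopic change is a secondary outcome (9.1), and 11.6 gives change in EREFS its own between-arm test.

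**The concern.** Blinding to treatment hides the arm. It does not hide the week-8 biopsy result, which the trial's hypothesis (9.4) expects to differ by arm. EREFS is a judgement made from images. A grader who knows that a subject's eosinophils have cleared may score borderline features lower, and one who knows they persist may score them higher. If more subjects clear on omeprazole, that tendency produces an EREFS difference between arms although the grader never learns the allocation.

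At stake is how the endoscopic result is read. A reader who sees EREFS and histology move together would naturally take one as support for the other. If the EREFS scores were informed by histology, part of that agreement is built in. Such bias cannot be taken out at analysis; it has to be prevented when the images are scored.

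**Working it through.** The plan gives no figure for EREFS (no SD, expected difference or power), so there is nothing of its own to reproduce. The calculation below is an illustration.

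**Inputs from the plan**
- 50 subjects per arm (11.4).
- Histologic response 50% on fluticasone alone and 70% to 80% on the combination (11.2). I use 75%, the midpoint, and show both ends.
- Two-sided 5% level. Section 11.2 gives alpha 0.05 for the primary outcome; I assume the same for EREFS.

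**Assumptions not in the plan**
- No true effect of omeprazole on EREFS.
- Knowing that a subject is a histologic responder lowers the score by d SD of EREFS change.
- The grader knows week-8 histology for a fraction k of subjects, the same in both arms.

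**Formulas**
- Spurious arm difference in SD units: e = d × k × (p₂ − 0.50).
- Standardised shift: λ = e × √(50/2) = 5e.
- Chance of a significant result: P(|Z + λ| > 1.96).

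**Results at 75% response**

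| d | k | e | λ | Rejection rate |
|---|---|---|---|---|
| 0.25 | 1 | 0.25 × 0.25 = 0.0625 | 0.3125 | 6.1% |
| 0.5 | 0.5 | 0.5 × 0.5 × 0.25 = 0.0625 | 0.3125 | 6.1% |
| 0.5 | 1 | 0.5 × 0.25 = 0.125 | 0.625 | 9.6% |
| 1 | 0.5 | 1 × 0.5 × 0.25 = 0.125 | 0.625 | 9.6% |
| 1 | 1 | 1 × 0.25 = 0.25 | 1.25 | 24% |

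**Across 70% to 80% response, all known (k = 1)**
- d = 0.25: 5.7% to 6.6%.
- d = 0.5: 7.9% to 11.7%.
- d = 1: 17% to 32%.

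**Which SD is meant.** The table takes d in units of the SD of the scores as recorded. If d is instead in units of the SD of unbiased scores, shifting only responders adds variance d²p(1 − p) in each arm, when k = 1. For d = 1 the variances become 1 + 0.25 = 1.25 and 1 + 0.1875 = 1.1875. Then λ = 0.25/√((1.25 + 1.1875)/50) = 1.13, and the rate is about 20% instead of 24%. For d = 0.5 the same step gives 9.3% instead of 9.6%. Hence the ranges 9-10% and 20-24%.

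**The case against.** **Access is not knowledge.** The schedule row refers to reviewing endoscopy findings. It does not mention EREFS scoring, nor its order relative to pathology. The only biopsy item in the same column is eotaxin-3 staining, and no section says when the week-8 eosinophil count is reported. A reader might infer that the PI will grade knowing the count; the documents show only that nothing prevents it. This stands, and it limits the claim to a possibility.

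**A single grader is not settled.** A reader might infer that the PI alone grades. Section 10.1 says so, but the schedule's PI/AI wording and the plural in 10.2 do not agree with it. If an associate investigator (AI) grades, the argument from file custody is weaker. That stands too, although the clinical record is another route to the count and no text masks an associate investigator.

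**The larger rates are upper scenarios.** They need histology known for every subject, a shift of 0.5 to 1 SD, and no true endoscopic effect beside a 25-point histologic one. This is right. With a 0.25 SD shift, or 0.5 SD and half of subjects known, the rate is about 6%. The inflation runs from near nil upward.

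**The consequence is limited.** The mechanism requires omeprazole truly to improve histology, so the primary conclusion would be correct. EREFS is one of several secondary outcomes, and the hypothesis in 9.4 names histology and symptoms, not endoscopy. A reader might infer that the blind or the primary endpoint is compromised; neither follows. What remains is that EREFS has its own between-arm test in 11.6.

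**Visit order is a separate matter.** A reader might infer that knowing which images are post-treatment also biases the comparison. It affects both blinded arms alike, so it does not create the arm difference described here. Baseline histology matters little as well, because every enrolled subject has already met the biopsy criterion (10.1).

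**Conclusion.** The point holds as a gap in the order of scoring for a secondary outcome. The plan lets the EREFS grader reach week-8 histology and symptom results before scoring, and blinding to arm does not close that route if histology differs by arm. Agreement between EREFS and histology could then be over-read.

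The size is unknown. Under the stated assumptions the false-positive rate for EREFS ranges from barely above 5% to 20-24% at 75% response, depending on how far the grader's scores move and for how many subjects the result is known. The direction does not depend on those assumptions; the magnitude depends on them entirely. The documents do not establish that the grader will have seen the results. The change is worth making because it is cheap and has to be in place before images are scored.

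**What to change.** In sections 10.1 and 10.2:

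- State that the grader scores each week-8 EREFS from the images, and that the score is locked and dated, before the grader views that subject's week-8 eosinophil count, eotaxin-3 score or questionnaire, in the study file or in AHLTA.
- State that week-8 histology, eotaxin-3 and questionnaire results are entered in the PI-held spreadsheet only after that lock.
- Reconcile the three descriptions of the grader (the PI in 10.1, PI/AI in the schedule, investigators in 10.2), and apply the same rule to whoever grades.

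Removing visit labels from the images is optional good practice; it does not address the between-arm mechanism.

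**Cost.** Protocol wording, one recorded date per subject, and a small delay in data entry or in the PI's access to results. No extra reader, procedure or patient contact is needed, and a single grader is kept. Masking stays incomplete where the PI performed the endoscopy or manages the patient. The recorded date at least allows those cases to be identified and a sensitivity analysis to be run without them.
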